### Suicidal ideation

When conducting studies with depressed patients, expression of suicidal ideation is a risk. We will address this risk in multiple ways. We will conduct a clinical evaluation prior to matching to assess the participant's appropriateness for the study in terms of depression severity and risk for suicidal ideation. In our previous work, expressions of suicidal ideation were rare because we assessed for depression severity and appropriateness for peer services during the initial clinical evaluation and such persons were excluded and referred for appropriate care. Also, peer mentors recruited for this study will receive training in a protocol for those participants who express suicidal ideation, to ensure the safety of the participants. If the participant

expresses suicidal ideation during a meeting, the peer mentor will immediately call the MHP who will call the participant and manage the situation. Assessment by the MHP may involve the following questions: (1) Do you have a desire to hurt yourself that you think you might act on? (2) Do you have a plan for hurting yourself and intend to carry the plan out? Participants may also be identified as a high risk for suicide if the participant reports a specific plan to commit suicide, or if the participant has risk factors for suicide. Risk factors may include multiple suicide attempts, moderate to severe depression, a high level of hopelessness, immediate access to a lethal method, a lack of reasons for living, psychosis or mania, poor social support or a recent stressful life event. Additional probing may be necessary to identify any other risk factors (e.g., access to a firearm). The MHP will ensure and facilitate urgent referral of high risk patients to the Emergency Department near their home where an evaluation to assess need for treatment is done. A geriatric psychiatrist ([name]) will be available for consultation in situations where the social worker needs assistance. In our experience, one instance of suicidal ideation (1 participant) did arise, the trained peer mentor contacted the PI who spoke with the participant and managed the situation without adverse events.

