## 1. Risks and Discomforts

### Psychosocial risks

We recognize that older individuals, especially those with chronic illness, can easily feel overwhelmed or fatigued by what would be minimally demanding tasks for others, and, therefore, we include this discomfort in the potential risks. A minority of participants may respond to certain interview questions with feelings of sadness and grief (e.g., upon being reminded of interpersonal problems and social isolation). To address undue emotional stress, multiple strategies were used to prevent adverse events: 1) rigorous screening of the older adult's appropriateness for a peer mentor intervention, performed by a mental health professional prior to matching, 2) rigorous training and continuous supervision of the peer to prevent escalating emotional distress, and 3) availability of professional staff to address peer mentor's concerns by phone at all times. In the event that the peer mentor needs assistance, the peer will contact the supervising MHP (with geriatric psychiatrist backup) who will speak with the participant regarding the problem. In our experience, peers have been able to detect signs in the participant of escalating distress and able to follow the established protocol without adverse events. Peer mentors will be trained to recognize and provide support to manage undue emotional distress. In the case that a participant is distressed, the peer mentor will listen actively, provide empathy and ask if they would like to speak with a mental health professional on the study team. If the participant answers in the affirmative, the PM will inform the MHP and the MHP will call the participant and conduct a clinical assessment with appropriate triage to connect with community or clinical resources. If the participant declines speaking with the MHP, the PM will inform the MHP during weekly supervision and also follow up with the participant at the next meeting. The MHP will be available by telephone during the week 9-5pm and a geriatric psychiatrist will be available in the case that the MHP is unable to manage the participant's distress.

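### The suicidal-ideation step sends the lay mentor to the mental health professional alone, with no written route when that person is off duty

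*Protocol*

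**What the plan says.** The Protocol's Suicidal ideation section covers ideation expressed during a meeting between mentor and participant. It gives the mentor one action: "the peer mentor will immediately call the MHP who will call the participant and manage the situation". The next urgent action belongs to the same person: "The MHP will ensure and facilitate urgent referral of high risk patients to the Emergency Department near their home". A geriatric psychiatrist "will be available for consultation in situations where the social worker needs assistance". The section also states that "peer mentors recruited for this study will receive training in a protocol for those participants who express suicidal ideation", but the content of that protocol is not in the documents.

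The preceding section, Psychosocial risks, deals with emotional distress. It lists among its safeguards that professional staff can be reached about mentors' "concerns by phone at all times". It directs a mentor who needs help to the supervising MHP, with a geriatric psychiatrist as backup. It then states: "The MHP will be available by telephone during the week 9-5pm", and adds that "a geriatric psychiatrist will be available in the case that the MHP is unable to manage" the participant's distress.

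The section on the supervisory role of the MHP gives mentors telephone access to the MHP as needed between supervision meetings, without stating hours. Under General Description of Study Design and Study Procedures (matching and scheduling of visits), the mentor contacts the participant and arranges the weekly chats. Neither section ties the chats to MHP hours.

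**The concern.** The mentor is a trained layperson, alone on a remote call, and has to act at once. Read literally, the step gives the mentor one contact and makes the Emergency Department referral depend on that same contact. If a chat takes place in the evening or at a weekend, the mentor could be calling someone who is off duty, and the referral would wait as well. Mentor and participant choose the time of the chat, so the text does not rule this out.

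At stake is the delay between a participant voicing suicidal thoughts and a clinician or emergency service responding. Participants enter with a PHQ-9 score of 10 or more, and the Protocol itself names suicidal ideation as a risk of studying depressed people. The initial assessment screens for it, but ideation can arise later, which is why the step exists. The point is about participant safety and does not touch the aims, endpoints, sample size or analysis.

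**Working it through.** This is a comparison of texts; the plan states no figure to reproduce.

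1. **Whom does the mentor call?** The Suicidal ideation section names the MHP. It does not use the word only, but it gives the mentor no other contact.

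2. **Who starts the Emergency Department referral?** The same section gives this to the MHP. It does not bar the psychiatrist from doing it, but it does not provide for it either.

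3. **When can the MHP be reached?** Three statements bear on this:
   - Psychosocial risks gives 9 to 5 during the week.
   - Psychosocial risks also promises professional staff by telephone at all times, without naming a role or a route.
   - The supervisory-role section says as needed, without hours.

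   The 9-to-5 sentence sits in the account of a distressed participant, so applying it to suicidal ideation is an inference. No other MHP hours are stated.

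4. **What is the psychiatrist's role?** In both risk sections the psychiatrist supports the MHP: for consultation when the social worker needs help, or when the MHP cannot manage the distress. The second wording could be stretched to cover an absent MHP, but neither is written as a contact for the mentor. In the one past event reported, the mentor contacted the principal investigator directly, and the situation was managed without adverse events. That is an account of experience; the current step does not instruct mentors to do the same.

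5. **Can a chat fall outside MHP hours?** Mentors arrange the times with participants, and no section sets a limit. The documents do not say how many chats, if any, are held out of hours.

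6. **Is there a route that bypasses the MHP?** None of these sections gives the mentor an emergency-services step. The separate training protocol may do so.

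The only arithmetic available describes the stated MHP hours. Nine to five is 8 hours a day, and a week has 7 × 24 = 168 hours.
- If the week means Monday to Friday (an assumption): 5 × 8 = 40 hours, and 40/168 = 23.8%.
- If it means every day: 7 × 8 = 56 hours, and 56/168 = 33.3%.

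These shares are not a measure of risk. The denominator includes nights, when chats are unlikely, and the figures leave out both the promised cover at all times and the psychiatrist backup.

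**The case against.** The strongest reply is that cover is already promised in the same part of the Protocol. Professional staff are to be available to mentors at all times, the MHP has psychiatrist backup, and neither sentence excludes suicidal ideation. On this view the 9-to-5 sentence belongs to a different scenario and should not govern, and the remaining fault is that one section does not repeat what the section before it says. This has force: it would be wrong to say that the Protocol has no out-of-hours cover. It does not answer the narrower point, because the promise names nobody to call, and the instruction that follows it again sends the mentor to the MHP. A mentor should not have to work out the route during an emergency.

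The training protocol may contain the full call sequence. That cannot be excluded. If it does, bringing the main text into line costs almost nothing.

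The Protocol also says, "In our previous work, expressions of suicidal ideation were rare", because people found unsuitable at the initial evaluation were excluded, and it reports one past instance. That limits the expected number of events but not the consequence of one that is mishandled.

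Routing the referral through a clinician is sensible in itself, since judging plan, intent and means is clinical work. The weakness is that no second clinician is named to do it.

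Finally, the SAP already reports post-study and three-month results, so an amendment cannot help participants who have finished. It would serve any who remain, and the intervention manual, which the Protocol says will be revised.

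**Conclusion.** The concern holds as a gap in the written urgent step, and it should be corrected. The step names the MHP alone for both the mentor's call and the Emergency Department referral. The cover promised in Psychosocial risks is not carried into it, and the mentor has no emergency-services step.

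No size can be put on the risk. The share of chats held out of hours is unknown, and the single past event comes without a denominator or a time of day.

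The conclusion rests on two readings: that the stated 9-to-5 hours also describe the MHP's availability for suicidal ideation, and that the unseen training protocol does not already supply the missing route. If the training protocol does supply it, what remains is to align the main text. Confidence is medium for these reasons. The case for acting is that the event is rare but urgent and the correction is cheap.

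**What to change.** Amend the Suicidal ideation section to set out the sequence:

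- The mentor calls the MHP at once.
- If the MHP is off duty or does not answer, the mentor calls the study's geriatric psychiatrist directly.
- If neither answers, or danger is imminent, the mentor calls emergency services.
- Whichever clinician takes the call may start the Emergency Department referral.

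Bring Psychosocial risks, the supervisory-role section and the mentors' training protocol into line, so that cover at all times has a named person behind it.

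An alternative is to require chats to be booked within MHP hours, keeping the emergency-services step.

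The cost is a few sentences of protocol text and some mentor training, using existing staff, with three practical demands. The psychiatrist must be reachable whenever an out-of-hours chat is booked. Because chats are remote, the mentor needs the participant's current location. Mentors also need a simple rule for recognising imminent danger, a judgement now left to the MHP. The alternative avoids out-of-hours psychiatrist cover for chats but makes scheduling less flexible.

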### **Confidentiality and privacy**

For participant participants, risks regarding breach of confidentiality and disclosure of clinical information exist and may be heightened due to use of non-professional peer mentors in the proposed study. Should confidentiality safeguards fail, there is potential harm in the form of social risks and disclosure of private information. However, the risks of participation should be no more than minimal, with effective confidentiality safeguards. The safeguards include the following: 1) Peer mentors sign a contract of confidentiality agreement before participating in the project, receive confidentiality training and the importance of confidentiality will be stressed throughout training and supervision sessions on a weekly basis. 2) Participant participants will be informed that absolute confidentiality cannot be guaranteed but study staff put rigorous procedures in place. In our experience, there were no known breaches of confidentiality in our pilot study or in our clinical trial, participants did not express concern about this during the consent process, and none dropped out of the study for this reason. All information collected will be coded with a study identification number and will be stored in secure servers that only IRB approved staff associated with the study can access. These records will be protected by the confidentiality system of MGH and are not disclosed except as required by law. Audio recordings are saved on a secure server, MGH OneDrive.

## **2. Benefits**

The proposed study could benefit the participant participants in terms of psychoeducation and self-care skills associated with depression, services delivered by a PM who is under a mental health professional's supervision. The peer may benefit from increased sense of self-efficacy in helping another person and have an increased knowledge base from the mental health training provided by the study. Benefits to society may include new knowledge regarding the provision of mental health services in the community. If the peer program is successful, new ways to provide depression care services in the community setting to low-income minority participants

are established. The risks to the patient for participating in this project are minimal and the possibility of improving depression care is substantial.

This research intends to inform the development of peer programs whose aim is to improve access and engagement of depression care among minority populations. Given that minority participants receive inadequate or no mental health care and are less likely to access traditional mental health services, developing novel methods of delivering depression services is important.

### **3. Statistical and Qualitative Analysis**

**Statistical analysis** We will screen data for quality and integrity. We will obtain descriptive statistics to characterize study participants. Percentage of session attended and engagement will be reported as percentages. Inferential analysis of depressive symptoms over time will be conducted using longitudinal linear regression taking into account clustering (via multi-level modeling) since peer mentors will meet with several patients. The quantitative data will identify measured factors that are related to engagement and depression reduction so that the mHealth components for peer delivery can be refined.

**Qualitative data analysis** All audio recordings will be professionally transcribed. The transcripts will be analyzed using thematic analysis which is a flexible and commonly used approach in qualitative analysis. The study team members will proceed through 4 phases: 1) immersion in the data by reading and re-reading the data, 2) generation of initial codes, 3) sorting of codes into themes, and 4) review and refinement of themes based on coded extracts and relevance to the entire dataset. The PI and members of the study team have conducted and published numerous qualitative studies and are experienced in qualitative methods. To ensure trustworthiness, the PI and trained study team members will code a subset of transcripts independently, compare their agreement on segments of coded data and resolve disagreements through in-depth discussion. The PI and study team members will meet on a weekly basis during the data analysis period to discuss in depth the rationale for coding and theme generation, and will resolve disagreements by negotiated agreement. Qualitative data analytic software, NVIVO11, (QSR Intl, Durham UK) will be used. The manual of the intervention will be revised based on review and analysis of the qualitative and quantitative data.

### **4. Monitoring and Quality Assurance**

**Research-Related Risks** [name] will lead weekly meetings to review study operations and compliance (e.g., data collection and management), to discuss any emerging concerns, to identify any training needs, and to address any human subjects issues. [name] and the study team will work to ensure compliance with study procedures.

- *Preparation:* An existing intervention manual (created for Peer Enhanced Depression Care) will be adapted for Peers plus, an intervention that integrates technology to deliver peer support. Any changes during the implementation is noted and noted,

- *Ongoing monitoring:* After each intervention meeting, PM activities will be reviewed by the mental health professional during weekly supervision meetings. All meetings will be audio-recorded. **Protocol Fidelity and Investigator Compliance.** The PI and team will record and report all protocol violations.

**Participant Confidentiality** All study materials will identify participants only by study ID, visit number, and visit date. The study research assistant will be trained in procedures to protect study participant confidentiality. Recordings of each PM-participant meeting will be immediately de-identified (e.g., only ID, visit number and date) and stored on a password protected computer; the recording will be made on zoom and stored on MGH dropbox. The research team will report to the IRB any instances of participant confidentiality breach and corresponding plans for corrective action.

**Data Validity and Security.** The research team will develop standard operating procedures for data collection, data management, and quality control. [name] will oversee all procedures related to secure data collection and management. Data activities will be conducted using (Research Electronic Data Capture (REDCap), a software and workflow tool for research data collection and management, with assistance from Partners HealthCare Research Computing, Enterprise Research Infrastructure & Services (ERIS) group. REDCap will provide secure web-based applications with an intuitive user interface data and real time validation rules.

## Privacy and Confidentiality

- Study procedures will be conducted in a private setting
- Only data and/or specimens necessary for the conduct of the study will be collected
- Data collected (paper and/or electronic) will be maintained in a secure location with appropriate protections such as password protection, encryption, physical security measures (locked files/areas)
- Specimens collected will be maintained in a secure location with appropriate protections (e.g. locked storage spaces, laboratory areas)
- Data and specimens will only be shared with individuals who are members of the IRB-approved research team or approved for sharing as described in this IRB protocol
- Data and/or specimens requiring transportation from one location or electronic space to another will be transported only in a secure manner (e.g. encrypted files, password protection, using chain-of-custody procedures, etc.)
- All electronic communication with participants will comply with Mass General Brigham secure communication policies
- Identifiers will be coded or removed as soon as feasible and access to files linking identifiers with coded data or specimens will be limited to the minimal necessary members of the research team required to conduct the research
- All staff are trained on and will follow the Mass General Brigham policies and procedures for maintaining appropriate confidentiality of research data and specimens

- The PI will ensure that all staff implement and follow any Research Information Service Office (RISO) requirements for this research
- Additional privacy and/or confidentiality protections

## **APPENDIX A**

### **Data Monitoring Committee / Data and Safety Monitoring Board Appendix**

---

A Data Monitoring Committee (DMC) or Data and Safety Monitoring Board (DSMB) will be convened for safety monitoring of this research study. The following characteristics describe the DMC/DSMB convened for this study (Check all that apply):

- The DMC/DSMB is independent from the study team and study sponsor.
- A process has been implemented to ensure absence of conflicts of interest by DMC/DSMB members.
- The DMC/DSMB has the authority to intervene on study progress in the event of safety concerns, e.g., to suspend or terminate a study if new safety concerns have been identified or need to be investigated.
- Describe number and types of (i.e., qualifications of) members:  
5 members  
1.Geriatric psychiatrist and researcher with experience of clinical trials of depression care interventions, NIH funded  
2.Geriatrician and researcher in mental health and use of paraprofessionals in medical care  
3.Social worker, PhD, health services research with expertise in peer support  
4.Statistician, PhD, with experience in NIH studies in geriatric mental health  
5.Study statistician, PhD, with experience in NIH studies in geriatric mental health
- Describe planned frequency of meetings  
DSMB meetings are held every 12 months.
- DMC/DSMB reports with no findings (i.e., “continue without modifications”) will be submitted to the IRB at the time of Continuing Review.
- DMC/DSMB reports with findings/modifications required will be submitted promptly (within 5 business days/7 calendar days of becoming aware) to the IRB as an Other Event.

**Study:**

Feasibility pilot study with approximately 32 participants  
Preliminary analysis of primary (PHQ-9) and secondary outcomes.

**Statistical Analysis**

Baseline characteristics, working alliance scores, and clinical and social outcomes were summarized. The Shapiro-Wilk test was applied to check the normality of each outcome measure. Paired-sample t-tests and Wilcoxon signed-rank test were conducted to assess the differences in outcome measures between baseline and post-study, as well as baseline and three-month follow-up scores, to determine statistical significance. For all analyses, a significance level of  $\alpha = 0.05$  was used for two-sided tests unless otherwise specified.

To assess the change in the primary outcome, depressive symptoms over time within the intervention group, a multilevel linear regression model was employed. This model included fixed effects for time points (e.g., baseline, post-intervention, and follow-ups) and covariates such as baseline loneliness, self-efficacy, working alliance scores, and demographic variables that might influence the intervention effects. Random intercepts and slopes were included to account for the repeated measures within participants, allowing for individual variability in both baseline levels and the trajectories of depressive symptoms over time. Additionally, random effects were specified at the peer coach level to account for the nested structure of the data, where participants were grouped by peer coaches. These analyses and data visualizations were conducted using R Statistical Software (v4.2.1; R Core Team 2022).

PHQ\_9

Model	Timepoint	Estimate	Std. Error	95% CI	p-Value	Effect Size(standardized coefficients)	Marginal R^2
Model 1: Basic	Baseline vs Poststudy	-1.93	0.79	(-3.513, -0.344)	0.018	-0.36	0.049
	Baseline vs 3-mons follow-up	-2.88	0.83	(-4.557, -1.209)	0.001	-0.54	
Model 2: Adjusted for demographics #	Baseline vs Poststudy	-1.93	0.79	(-3.509, -0.348)	0.018	-0.36	0.159
	Baseline vs 3-mons follow-up	-2.81	0.83	(-4.488, -1.137)	0.001	-0.53	
Model 3: Full Model ##	Baseline vs Poststudy	-1.78	0.77	(-3.336, -0.230)	0.025	-0.33	0.276
	Baseline vs 3-mons follow-up	-2.42	0.81	(-4.057, -0.784)	0.005	-0.45	

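### The protocol plans inference only for depressive symptoms; the SAP also tests three secondary outcomes at an uncorrected 0.05 and should label those results exploratory

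*SAP*

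**What the plan says.** The protocol (3. Statistical and Qualitative Analysis) commits to one inferential analysis: "Inferential analysis of depressive symptoms over time will be conducted using longitudinal linear regression", with clustering by peer mentor. Attendance and engagement are to be reported as percentages. A further sentence is a search for correlates, not a test of change in other outcomes: "The quantitative data will identify measured factors that are related to engagement and depression reduction".

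The SAP (Study) describes a feasibility pilot of about 32 participants and a "Preliminary analysis of primary (PHQ-9) and secondary outcomes". Its Statistical Analysis section is in the past tense ("a multilevel linear regression model was employed") and is followed by tables of estimates, standard errors, confidence intervals and p-values. On testing it says:

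- "Paired-sample t-tests and Wilcoxon signed-rank test were conducted to assess the differences in outcome measures", and these differences were tested "between baseline and post-study, as well as baseline and three-month follow-up scores, to determine statistical significance".
- "For all analyses, a significance level of" 0.05 "was used for two-sided tests unless otherwise specified".

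The text introduces the multilevel model for the primary outcome only. The tables nevertheless give multilevel results for PHQ-9, self-efficacy, emotional well-being and social function, each at post-study and 3 months, under three models (basic, demographics, demographics plus loneliness). The SAP states no multiplicity rule, lead visit, lead model or order among the secondary outcomes.

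**The concern.** Three things combine. Tests of change in the secondary outcomes are not in the protocol. The SAP cannot show that they were prespecified, because its text already holds the results. And every contrast is read against the same 0.05.

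The lead analysis is also open. The covariates in the SAP text (baseline loneliness, self-efficacy, working alliance, demographics) match none of the three tabulated models. Paired t-tests and Wilcoxon tests cover the same changes, with no rule for which result decides.

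What is at stake is how a small uncontrolled pilot is read. Of the 18 secondary p-values printed, 15 are below 0.05; the exceptions are social function at post-study in each model. A reader who takes these at face value would credit the programme with established gains in self-efficacy and emotional well-being at the end of the intervention, and those are the results most sensitive to how many contrasts were examined.

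**Working it through.** **Inputs.** Estimates and standard errors come from the SAP tables, and the level is 0.05 two-sided. Degrees of freedom are not stated. The printed confidence limits imply them: for self-efficacy post-study in Model 1, half-width/SE = (3.686 − 0.375)/2/0.824 = 2.009, which is the t quantile at about 49 df. I used 48 and checked 40 to 55.

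**Reproducing the printed p-values (Model 1, t = estimate/SE, 48 df).**

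| Contrast | t | p recomputed | p printed |
|---|---|---|---|
| Emotional well-being, 3 months | 12.566/2.869 = 4.38 | 0.00006 | 0.000 |
| Social function, 3 months | 18.775/4.994 = 3.76 | 0.00046 | 0.001 |
| Self-efficacy, 3 months | 2.773/0.870 = 3.19 | 0.0025 | 0.003 |
| Self-efficacy, post-study | 2.030/0.824 = 2.46 | 0.0174 | 0.017 |
| Emotional well-being, post-study | 6.571/2.668 = 2.46 | 0.0174 | 0.017 |
| Social function, post-study | 5.804/4.656 = 1.25 | 0.219 | 0.219 |

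The SAP's figures are reproduced to within about 0.001.

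**Size of the family.** Models 1 to 3 re-estimate the same contrasts on the same people, so the natural family is 3 outcomes × 2 visits = 6. If independent, the chance of at least one false positive is 1 − 0.95^6 = 0.265. With simulated equicorrelated normal statistics it is 0.24, 0.21 and 0.16 at assumed correlations of 0.3, 0.5 and 0.7. The documents give no correlation.

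**Holm over the six, Model 1.** The step limits are 0.05/6 = 0.0083, 0.05/5 = 0.0100, 0.05/4 = 0.0125 and 0.05/3 = 0.0167. The three 3-month contrasts pass the first three steps. Self-efficacy post-study (0.0174) fails the fourth, and the procedure stops there. Its adjusted value is 3 × 0.0174 = 0.052, and emotional well-being post-study takes the same value.

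**Holm-adjusted values by model.**

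| Contrast | Model 1 | Model 2 | Model 3 |
|---|---|---|---|
| Emotional well-being, 3 months | 0.0004 | 0.0005 | 0.0013 |
| Social function, 3 months | 0.0023 | 0.0030 | 0.0085 |
| Self-efficacy, 3 months | 0.010 | 0.010 | 0.022 |
| Self-efficacy, post-study | 0.052 | 0.052 | 0.061 |
| Emotional well-being, post-study | 0.052 | 0.052 | 0.087 |
| Social function, post-study | 0.219 | 0.218 | 0.205 |

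From 40 to 55 df, no contrast crosses 0.05 in any model.

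**Sensitivity to the procedure (two failing post-study contrasts).**

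- Model 1: Hochberg gives 2 × 0.0174 = 0.035 and Benjamini-Hochberg gives (6/5) × 0.0174 = 0.021, so both pass. Model 2 is the same in substance (0.036 and 0.021 to 0.022).
- Model 3: Hochberg gives 0.061 (self-efficacy) and 0.087 (emotional well-being). Benjamini-Hochberg gives 0.031 and 0.052.

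**PHQ-9.** In its own two-visit family, both contrasts pass Holm in every model (printed p at most 0.005 at 3 months and 0.025 post-study, against limits of 0.025 and 0.05). If all eight Model 1 contrasts were pooled, PHQ-9 post-study would have a Holm value of 4 × 0.0174 = 0.070. Whether it survives therefore depends on treating the primary outcome separately.

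**The case against.** The strongest reply is that this is a pilot labelled preliminary, with PHQ-9 named primary and the others secondary. Every contrast carries an estimate and a 95% CI, the null social function results are shown, and no sentence claims significance for a secondary outcome. Self-efficacy and emotional and social function were planned measures in the protocol. Familywise control is often not asked of secondary outcomes in a pilot.

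Much of this stands. A lead outcome is named, and strict correction is not required here. But the label does not say which p-values fall outside the protocol's planned inference, and the SAP's own stated purpose for the tests is to settle significance at 0.05.

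Four stronger readings go beyond the documents:

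- A reader might infer that none of the secondary results is supported. The 3-month results for all three outcomes survive Holm in every model, and the Model 1 post-study misses are narrow and specific to Holm.
- A reader might count 18 or 24 separate tests and quote error rates of 60% or 71%. Those figures assume independence, and three re-fits of the same data are far from independent.
- A reader might conclude that the secondary tests were chosen because of the results. The documents show only that the SAP text postdates the results and that the protocol is silent on these tests.
- A reader might want PHQ-9 post-study in Model 1 made the single lead contrast. No section supports that choice. It would be made after the data were seen, and it would drop the 3-month contrast from an analysis planned over time.

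**Conclusion.** The point holds as one of labelling and disclosure. The secondary tests lie outside the inference planned in the protocol, are uncorrected, and sit in a document written after the results.

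Within one model the chance of at least one false positive is about 26% under independence and about 24% to 16% at assumed correlations of 0.3 to 0.7. In numerical terms, two of the five nominally significant secondary contrasts per model fail Holm (self-efficacy and emotional well-being, post-study) and three survive (all at 3 months).

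This rests on a family of six and on degrees of freedom inferred from the confidence limits. The family may be larger: the protocol also measures coping, loneliness and physical function, for which the SAP has no results table. With an assumed 12 contrasts the Bonferroni limit is 0.05/12 = 0.0042. Emotional well-being and social function at 3 months still pass in every model. Self-efficacy at 3 months passes in Models 1 and 2 (printed 0.003) but not in Model 3 (0.006). No correction makes an unplanned test a planned one, so the 3-month results are also exploratory.

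**What to change.** In the SAP's Statistical Analysis section:

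1. State that the text was written after the results were available, and that the protocol planned inference only through the longitudinal model of PHQ-9.
2. Limit the 0.05 rule to PHQ-9 over time, keeping both the post-study and 3-month contrasts.
3. Report self-efficacy, emotional well-being and social function as exploratory estimates with 95% CIs. Label any p-values unadjusted and draw no significance conclusion from them.
4. Present Models 1 to 3 as re-fits of the same contrasts. If one is called the lead, say that it was chosen after the data were seen.

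This needs no new data or analysis. The cost is SAP and report wording, and secondary results that are stated less favourably.
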